10.3. Subgroup Analysis

Appropriate subgroup analyses will be conducted for primary and selected secondary efficacy endpoints by the following subgroups for Phase 2:

1. Age groups (< 65 years, ≥ 65 to < 75 years, ≥ 75 years);
2. Gender (male and female);
3. Region (US, Non-US);
4. Race (white vs non-white);
5. Baseline cytogenetic risk status (better-risk, intermediate-risk, poor-risk, failure);
6. For IDH2 mutated subjects, IDH2 gene mutation sub-type (R140Q vs. R172K);
7. AML initial diagnosis: (primary or secondary);
8. WHO classification of AML;
9. ECOG performance status at baseline (Grade 0, 1, 2);
10. European LeukemiaNet (ELN) risk classification (favorable, intermediate and adverse).

A forest plot will be provided displaying the hazard ratios (for time to event endpoints) and odds ratios (for ORR) and their 95% CIs, obtained from Cox proportional hazards and logistic regression models, respectively, for each subgroup.

Subgroup analyses will be conducted for the following efficacy endpoints:

- Overall Response Rate;
- Overall Survival.

11. SAFETY ANALYSIS

All analyses of safety data will be conducted using the safety population unless otherwise specified, separately for Phase 1b and Phase 2. Safety summaries will be provided by dose cohort (Phase 1b), and treatment arm (Phase 2), and overall (Phase 1b and Phase 2 separately).

For summaries of safety data, the treatment period is defined as follows:

date of first dose through date of last dose + 28 days.

No inferential statistical analyses will be conducted on the safety data.

11.1. Adverse Events

Adverse events (AEs) will be analyzed in terms of treatment-emergent adverse events (TEAEs) which are defined as any AEs that begin on or after the start of study drug through 28 days after the last study treatment. All AEs will be coded using the Medical Dictionary for Regulatory Affairs® (MedDRA) Version 22.0. The severity will be graded by the study personnel based on National Cancer Institute (NCI) Common Terminology Criteria for Adverse Events (CTCAE) Version 4.03.

A treatment-related TEAE is defined as TEAE that is assessed by the Investigator to be possibly related to AG120/AG221 or AZA.

[figure not shown]
If a subject experiences the same AE more than once with different toxicity grade, then the event with the highest grade will be tabulated in “by grade” tables. If a subject experiences multiple AEs under the same PT (SOC), then the subject will be counted only once for that PT (SOC).

[figure not shown]
The number of subjects with at least one TEAE will be summarized. The incidence of TEAEs will be summarized by MedDRA SOC and PT. Tables summarizing the incidence of TEAEs will be generated for each of the following:

- Summary of TEAEs
- All TEAEs;
- TEAEs Exposure Adjusted Incidence Rate (EAIR), only for Phase 2;
- TEAEs by Cycle, only for Phase 2;
- TEAE by decreasing frequency of PT;
- TEAEs related to study drug;
- TEAEs by maximum severity;
- TEAEs with CTCAE grade 3 or;
- Related TEAEs with CTCAE grade 3 or 4;
- Serious TEAEs;
- Serious TEAEs related to study drug;
- Serious TEAEs EAIR, only for Phase 2;
- Serious TEAE by decreasing frequency of PT, only for Phase 2;

- TEAEs leading to study drug withdrawn;
- TEAEs related to study drug and leading to study drug withdraw;
- TEAEs with leading to dose reduction;
- TEAEs related to study drug and leading to study drug dose reduction;
- TEAEs leading to study drug dose interruption;
- TEAEs related to study drug and leading to study drug dose interruption;
- All TEAEs resulting in death;
- Related TEAEs resulting in death;
- TEAEs leading to death EAIR, only for Phase 2;
- TEAEs for the following baseline subgroups (provided when the number of subjects are sufficient), only for Phase 2:
 - Gender (male and female);
 - Age (< 65 years, ≥ 65);
 - Baseline ECOG performance status (Grade 0, 1, 2);
 - Baseline ANC value ($\leq 0.5 \times 10^9/L$, $0.5 < 1 \times 10^9/L$, $\geq 1 \times 10^9/L$)
 - Baseline creatinine clearance value (<45, 45-<60, ≥60 mL/min);

Listings for the corresponding summary tables will be presented separately. Non-treatment-emergent AEs will also be included in one of the listings.

11.3. Death

System organ classes (SOCs) and preferred terms (PTs) are coded using the MedDRA dictionary (Version 22.0). Cause of death will be coded as well using the same MedDRA dictionary. Cause of death will be summarized in the Safety population with the following categories:

- On-treatment death: Deaths within 28 days of the last dose of study drug.
- Post-treatment death: Deaths on or after 28 days of the last dose of study drug.
- Overall: All death

On-treatment deaths, post-treatment deaths and all deaths will also be summarized by SOC and PT. A listing will be provided including deaths for all screened subjects.

11.4. Clinical Laboratory Evaluations

Clinical laboratory results will be summarized descriptively by dose cohort (Phase 1b) or treatment arm (Phase 2), which will also include a display of change from baseline. Laboratory values outside of the normal ranges will be identified. Normal ranges will be used to determine the categories of High, Low, and Normal for laboratory tests that have no severity grade.

Clinically significant hematologic and non-hematologic laboratory abnormalities that meet Grade 3 or Grade 4 criteria according to the NCI CTCAE 4.03 will be summarized. The worst grade during the treatment period will be summarized by dose cohort (Phase 1b) and treatment

arm (Phase 2). Frequency distributions of CTC grade that shift from baseline to the worst grade during treatment period will be presented by treatment arm when data is applicable. Graphical display of select laboratory parameters over the course of the study will be provided where useful to assist in the interpretation of results.

Listings of all clinical laboratory data from central laboratory with abnormal flags will be provided by subjects and tests. Listings will also be provided for the local laboratory data.

11.4.1. Hematology

For hematologic parameters, the change from baseline will be summarized by study visit and by treatment arm for Phase 2.

Shifts in CTC grades from baseline to worst grade, separated by worst (high) and worst (low) assessments, will be summarized by dose cohort (Phase 1b) and treatment arm (Phase 2) for hemoglobin, platelet counts, ANC, WBC, and RBC.

In addition, figures for the mean of hemoglobin, platelet counts, ANC, WBC and RBC by visit will be provided by treatment arm for Phase 2.

11.4.2. Serum Chemistry

For serum chemistry parameters, the change from baseline will be summarized by study visit and by treatment arm for Phase 2.

Shifts in CTC grades from baseline to worst grade will be summarized by dose cohort (Phase 1b) and treatment arm (Phase 2).

The proportion of subjects with clinically significant post-baseline change in hepatic, renal function and electrolytes will be assessed based on the criteria presented in the [Table 5](#).

Table 5 Serum Chemistry Changes of Interest

Chemistry Laboratory Test	Parameters for any value and the last value
ALT	ALT \geq \times 3ULN (presented as \geq 3- < \times 5 ULN, \geq 5- < \times 8 ULN and \geq 8ULN)
AST	AST \geq \times 3ULN (presented as \geq 3- < \times 5 ULN, \geq 5- < \times 8 ULN and \geq 8ULN)
Bilirubin Total	Bilirubin Total \geq \times 2ULN Bilirubin Total \geq \times 3ULN
Total Bilirubin and ALT	Composite of Total Bilirubin \geq \times 2ULN and ALT \geq \times 3ULN (ALT presented as \geq 3 - < \times 5 ULN, \geq 5 < \times 8 ULN and \geq 8 ULN) concurrent and within 1 cycle of Total Bilirubin elevation and at any time after start of treatment
Total Bilirubin and AST	Composite of Total Bilirubin \geq \times 2ULN and AST \geq \times 3ULN, (AST presented as \geq 3 < \times 5 ULN, \geq 5 < \times 8 ULN and \geq 8 ULN) concurrent and within 1 cycle of Total Bilirubin elevation and at any time after start of treatment
Potassium	Hypokalemia < 3.0 mmol/L and >15% decrease from BL Hyperkalemia > 6.0 mmol/L and >15% increase from BL
Potassium and Uric acid	Composite of concurrent hyperkalemia (potassium >ULN and >25% increase from BL) and hyperuricemia (uric acid >ULN and >25% increase from BL)
Phosphorus and Uric acid	Composite of concurrent hyperphosphatemia (phosphorus >ULN and >25% increase from BL) and hyperuricemia (uric acid >ULN and >25% increase from BL)
Calcium and Uric acid	Composite of concurrent hypocalcemia (calcium <ULN and >25% decrease from BL) and hyperuricemia (Uric acid >ULN and >25% increase from BL)
Magnesium	Hypomagnesemia Grade \geq 2 and >25% decrease from BL

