### 4.2. Inclusion Criteria

Subjects must satisfy the following criteria to be enrolled in the study:

1. Subject is  $\geq 18$  years of age at the time of signing the informed consent form (ICF).
2. Subject must understand and voluntarily sign an ICF prior to any study-related assessments/procedures being conducted.
3. Subject is willing and able to adhere to the study visit schedule and other protocol requirements.
4. Subject has newly diagnosed, primary (ie, de novo) or secondary (progression of MDS or myeloproliferative neoplasms [MPN], or therapy-related) AML according to the WHO classification ([Appendix B](#)) with  $\geq 20\%$  leukemic blasts in the bone marrow:
  - a. Have an IDH1 or IDH2 gene mutation (R132, R140, or R172)
    - o IDH mutational status will be assessed locally; for sites without local testing capabilities, a referral lab will be identified
  - b. By the investigator's assessment who are not candidates to receive intensive IC
5. Subject has an Eastern Cooperative Oncology Group (ECOG) performance status of 0, 1 or 2 ([Appendix D](#)).
6. Subject has adequate organ function defined as:
  - Serum aspartate aminotransferase/serum glutamic oxaloacetic transaminase (AST/SGOT) and alanine aminotransferase (ALT/SGPT)  $\leq 3 \times$  ULN, unless considered due to leukemic organ involvement.
  - Serum total bilirubin  $< 1.5 \times$  ULN. Higher levels are acceptable if these can be attributed to ineffective erythropoiesis,  $\leq 3$  times the upper limit of normal for Gilbert's syndrome (eg, a gene mutation in UGT1A1), or leukemic organ involvement.
  - Serum creatinine  $< 2 \times$  ULN or creatinine clearance  $> 30$  mL/min based on the Modification of Diet in Renal Disease (MDRD) glomerular filtration rate (GFR):  
$$\text{GFR (mL/min/1.73 m}^2\text{)} = 175 \times (\text{S}_{\text{cr}})^{-1.154} \times (\text{Age})^{-0.203} \times (0.742 \text{ if female}) \times (1.212 \text{ if African American})$$
7. Agree to serial bone marrow aspirate/biopsies.

8. Females of childbearing potential (FCBP)\* may participate, providing they meet the following conditions:

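### The liver rows of SAP Table 5 are labelled post-baseline change but carry no baseline condition, so some subjects who enter at or above a cut-off would be counted as changed without worsening

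*SAP*

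**What the plan says.** SAP 11.4.2 introduces its table of serum chemistry changes of interest with "The proportion of subjects with clinically significant post-baseline change in hepatic, renal function and electrolytes will be assessed based on the criteria presented in" Table 5. The column of criteria is headed "Parameters for any value and the last value".

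The liver rows are ALT at least 3 x ULN and AST at least 3 x ULN (each shown in bands 3 to <5, 5 to <8, and 8 or more), and total bilirubin at least 2 x ULN and at least 3 x ULN. Two composites combine bilirubin at least 2 x ULN with ALT or AST at least 3 x ULN. The composites add a timing condition, "concurrent and within 1 cycle of Total Bilirubin elevation and at any time after start of treatment". None of these rows refers to baseline.

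The other rows do. Potassium, for example, is "Hypokalemia < 3.0 mmol/L and >15% decrease from BL", and the combined electrolyte and uric acid rows and the magnesium row each require a change of more than 25%. The lipid criteria in SAP 11.4.5, Table 6, require a rise of more than 10%.

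Protocol 4.2, inclusion criterion 6, sets AST and ALT at no more than 3 x ULN, "unless considered due to leukemic organ involvement". Bilirubin must be below 1.5 x ULN, but "Higher levels are acceptable if these can be attributed to ineffective erythropoiesis". It may also be up to 3 x ULN in Gilbert's syndrome, and leukemic organ involvement is a further exception.

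**The concern.** A table described as change should count subjects who changed. Here a subject can satisfy a liver criterion before the first dose and satisfy it again on treatment with a value that is the same or lower. The result mixes abnormality present at entry with abnormality that arose on treatment, and the table does not let a reader separate them.

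Bilirubin is where this matters most. Protocol 8.2 describes AG-221 as an inhibitor of UGT1A1, and Protocol 3.1.1.3 and 7.2.2.3.2 treat bilirubin rises in subjects with a UGT1A1 mutation separately. Criterion 6 lets subjects with Gilbert's syndrome enter at up to 3 x ULN, which is above the 2 x ULN row.

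**Working it through.** The plan states no figure for this point, so there is none to reproduce. The check compares the cut-offs with eligibility, applies the rows literally to example subjects, and then sizes the effect under stated assumptions.

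**1. Cut-offs against eligibility (multiples of ULN).**

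| Row (SAP Table 5) | Cut-off | Baseline condition | Usual entry limit (Protocol 4.2) | Exceptions |
|---|---|---|---|---|
| ALT, AST | ≥3 | none | ≤3 | no upper limit stated for leukemic involvement |
| Total bilirubin | ≥2; ≥3 | none | <1.5 | ≤3 in Gilbert's syndrome; no number stated for ineffective erythropoiesis; leukemic involvement |
| Composites | bilirubin ≥2 with ALT or AST ≥3 | none (timing only) | both limits above | bilirubin needs an exception; ALT or AST must be at the limit or excepted |

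The bilirubin sentence could be read as applying the 3 x ULN cap to leukemic involvement as well. Under either reading, entry at or above 2 x ULN is possible. ALT or AST of exactly 3.0 x ULN needs no exception, because the entry limit and the cut-off both include that value.

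**2. Literal application to subjects who do not worsen.**

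| Baseline to post-baseline (x ULN) | Counted under Table 5 |
|---|---|
| Gilbert's, bilirubin 2.5 to 2.5 | yes, ≥2 row |
| Gilbert's, bilirubin 3.0 to 2.1 | yes, ≥2 row |
| ALT 3.0 to 3.0, no exception used | yes, 3 to <5 band |
| Leukemic involvement, ALT 6 to 4 | yes, 3 to <5 band |
| ALT 6 and bilirubin 4 (both excepted) to ALT 4 and bilirubin 2.5 | yes, composite |

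**3. Size.** Let q be the share at or above a cut-off at baseline with at least one post-baseline value still at or above it, and r the new-onset rate among the rest. The documents give neither, so both are assumptions.

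Reported proportion = q + (1 − q)r. Counting new onset only, over all subjects, gives (1 − q)r.

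The table uses r = 10%. The counts use the planned minimum arm sizes of 66 and 33.

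| q | Reported | New onset only | Non-new share of those reported, q / [q + (1 − q)r] | Non-new subjects among 66 | Among 33 |
|---|---|---|---|---|---|
| 2% | 0.02 + 0.98 × 0.10 = 11.8% | 9.8% | 17% | 1.3 | 0.7 |
| 5% | 0.05 + 0.95 × 0.10 = 14.5% | 9.5% | 34% | 3.3 | 1.7 |
| 10% | 0.10 + 0.90 × 0.10 = 19.0% | 9.0% | 53% | 6.6 | 3.3 |

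With r from 5% to 20%, the non-new share runs from 29% down to 9% at q = 2%, from 51% to 21% at q = 5%, and from 69% to 36% at q = 10%.

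**4. Between arms.** With the same q in both arms, the reported difference is (1 − q)(r1 − r0). At q = 5% a true 10-point difference is reported as 0.95 × 10 = 9.5 points. Randomization balances q in expectation, so what remains in Phase 2 is chance imbalance: one extra control subject moves that arm by 1/33 = 3.0 points. In a Phase 1b dose-finding cohort of 3 to 6, one subject moves the rate by 1/3 to 1/6, or 33 to 17 points.

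**The case against.** The strongest reply is that baseline is reported elsewhere. SAP 11.4.2 plans shifts in CTC grade from baseline to worst for both phases, and change from baseline by visit for Phase 2. SAP 11.4 adds a general change-from-baseline display and by-subject listings of all central laboratory data. A subject whose bilirubin falls from 2.5 to 2.1 x ULN can be found there. This stands as mitigation but does not correct Table 5. The shift tables use grades rather than the Table 5 bands and take one analyte at a time, so they cannot show whether a composite was already present at entry. Summaries by visit do not identify individuals, and the listings would have to be reassembled by hand.

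Second, absolute ULN multiples are a legitimate display of liver abnormality. They leave out nobody with a high value, and the protocol itself uses an unconditioned ALT trigger of 3 x ULN for liver monitoring (7.2.2.3.2 and Appendix P). This is right. The fault lies in calling the result a change without splitting it by baseline, not in the cut-offs.

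Third, the number affected may be close to zero. Apart from ALT or AST of exactly 3.0 x ULN, entry above a cut-off needs a named exception. Meeting a composite needs a bilirubin exception together with a transaminase at its limit or excepted. This also stands.

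A reader might infer that the Phase 2 liver comparison is biased, or that a drug signal will be hidden or imitated. The documents do not support that. They give no share above the cut-offs at entry, randomization leaves only chance imbalance between arms, and SAP 11 plans no inferential analysis of safety data. The 3.0-point step is simply one subject in 33 and applies to any yes/no safety item in that arm.

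**Conclusion.** The point holds as a defect of labelling and presentation. As written, the ALT, AST, bilirubin and composite rows of Table 5 do not measure what the lead-in sentence says they measure, and eligibility makes the discrepancy possible in practice. That much rests on the text alone.

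The size rests on assumed values of q and r. For q of 2 to 10% the overstatement relative to new onset over all subjects is q itself, that is 2 to 10 percentage points, and the true q could be lower. It matters most in the small, non-randomized Phase 1b cohorts. The consequence is confined to descriptive safety reporting: the primary response-rate analysis, its two-sided 0.2 level, its power and its sample size do not depend on these rows.

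**What to change.** Change SAP 11.4.2 as follows.

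- Keep the absolute rates for any value and last value, but label the liver rows as post-baseline abnormal values rather than change.
- For each liver row and each composite, add a table of baseline category (below, or at or above, the cut-off) by worst post-baseline category in the Table 5 bands. For a composite, take at or above to mean that both components meet their cut-offs at baseline.
- Report as new-onset change only subjects below the cut-off at baseline who cross it.
- Show subjects at or above the cut-off at baseline separately with their worst post-baseline band. The top bands are open-ended, so list the baseline and worst values for these subjects too; otherwise a rise within the top band would not show.

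A rule that counts subjects already above the cut-off only if they reach at least twice baseline should not be used. The factor has no basis in the documents. A subject with Gilbert's syndrome who rises from 3.0 to 5.9 x ULN would be dropped, since 2 × 3.0 = 6.0, although the protocol says that more than 5 x ULN in subjects with a UGT1A1 mutation may be considered a dose-limiting toxicity (3.1.1.3) or clinically significant (7.2.2.3.2).

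The cost is SAP wording, programming and one more table, with new-onset rates slightly lower than the absolute ones. No new data are needed. The protocol's amendment justification says that the primary clinical study report is final, so the table could be issued as a supplement.

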Q3	Third Quartile
QTcB	Heart-Rate Corrected QT with Bazett’s Correction
QTcF	Heart-Rate Corrected QT with Fredericia’s Correction
RBC	Red blood Cells

Abbreviation or Specialist Term	Explanation
RCD	Recommended Combination Dose
SAE	Serious Adverse Event
SAP	Statistical Analysis Plan
SC	Subcutaneous
SD	Stable Disease
SGPT	Serum Glutamic Pyruvic Transaminase
SOC	System Organ Class
TEAE	Treatment Emergent Adverse Event
TTO	Time Trade-off
ULN	Upper Limit of Normal
VAS	Visual Analogue Scale
WBC	White Blood Cells
WHO	World Health Organization

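### SAP Table 5 ties hypocalcemia to the upper limit of normal, so a calcium fall of more than 25% that ends within the normal range can count as hypocalcemia

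*SAP*

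**What the plan says.** SAP Section 11.4.2 gives Table 5 an operative role: "The proportion of subjects with clinically significant post-baseline change in hepatic, renal function and electrolytes will be assessed based on the criteria presented" there. The criteria apply both to any post-baseline value and to the last value.

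The calcium part of the calcium and uric acid row is "Composite of concurrent hypocalcemia (calcium <ULN and >25% decrease from BL". The uric acid part is the same as in the phosphorus row, apart from a capital letter: "and hyperuricemia (uric acid >ULN and >25% increase from BL". The two parts must be concurrent. The SAP's list of abbreviations expands ULN as "Upper Limit of Normal" and has no entry for a lower limit.

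The neighbouring rows are:

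- High-direction composites: "Composite of concurrent hyperkalemia (potassium >ULN and >25% increase from BL" and "Composite of concurrent hyperphosphatemia (phosphorus >ULN and >25% increase from BL".
- Low-direction rows: "Hypokalemia < 3.0 mmol/L and >15% decrease from BL" and "Hypomagnesemia Grade \geq 2 and >25% decrease from BL".

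Neither the SAP nor the protocol gives another calcium limit for this composite, and neither gives a calcium reference range.

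**The concern.** Every normal calcium value lies below ULN, so the limit in the calcium row does not describe a low value. The rest of the table points to a slip. The high-direction composites use >ULN, as they should, and the other two low-direction rows use a low cut-off or a severity grade. The calcium row reads like one of its neighbours with the inequality reversed and the limit left unchanged.

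A programmer following the table would code <ULN. At stake is agreement between one row and its label, and between outputs. SAP Section 11.4 says that values outside the normal range will be identified and that central laboratory listings will carry abnormal flags. A subject could therefore count as hypocalcemic in this row while the listing shows no low calcium.

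**Working it through.** The plan states no figure for this criterion, so there is none to reproduce. The check is a comparison of two rules. Let B be baseline calcium and P a post-baseline value.

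- Written rule: P < ULN and P < 0.75 × B.
- Lower-limit rule: P < LLN and P < 0.75 × B.

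The uric acid condition is identical in both and is taken as met.

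**Where the rules differ.** They disagree only when LLN ≤ P < ULN and P < 0.75 × B. Such a P exists only if 0.75 × B > LLN, that is, B > LLN/0.75.

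**What the ULN clause removes.** Among subjects with a fall of more than 25%, it excludes only those with P ≥ ULN. That needs B > ULN/0.75 = 1.33 × ULN.

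**Baselines at or below ULN.** Here a fall of more than 25% gives P < 0.75 × ULN. If 0.75 × ULN is below LLN, every such P is low and the two rules agree.

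The reference ranges below are assumptions.

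| Assumed LLN–ULN | 0.75 × ULN | Below LLN? | LLN/0.75 (as multiple of ULN) | ULN/0.75 |
|---|---|---|---|---|
| 8.4–10.2 mg/dL | 7.65 | yes | 11.20 (1.098) | 13.60 |
| 8.5–10.5 mg/dL | 7.88 | yes | 11.33 (1.079) | 14.00 |
| 8.6–10.2 mg/dL | 7.65 | yes | 11.47 (1.124) | 13.60 |
| 8.8–10.6 mg/dL | 7.95 | yes | 11.73 (1.107) | 14.13 |
| 2.10–2.55 mmol/L | 1.91 | yes | 2.80 (1.098) | 3.40 |
| 2.15–2.50 mmol/L | 1.88 | yes | 2.87 (1.147) | 3.33 |
| 2.20–2.60 mmol/L | 1.95 | yes | 2.93 (1.128) | 3.47 |

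**Worked cases**, assumed range 8.5–10.5 mg/dL:

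| Baseline → post | Fall | Written rule | Lower-limit rule |
|---|---|---|---|
| 13.0 → 9.5 | 3.5/13.0 = 26.9% | met | not met |
| 12.5 → 9.2 | 3.3/12.5 = 26.4% | met | not met |
| 11.0 → 9.0 | 2.0/11.0 = 18.2% | not met | not met |
| 10.5 → 7.8 | 2.7/10.5 = 25.7% | met | met |
| 9.5 → 7.0 | 2.5/9.5 = 26.3% | met | met |
| 14.5 → 10.8 | 3.7/14.5 = 25.5% | not met | not met |

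The first two cases show the fault: a normal value counted as hypocalcemia. The third shows that a fall from high to normal is not enough without the 25% condition. The last shows the only situation in which the ULN clause excludes anyone.

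**The case against.** The strongest reply is that the limit hardly matters, because the 25% fall does the screening. That is largely right. Since <ULN excludes almost nobody on its own, a reader might infer that the row would flag nearly everyone, or that any fall from high to normal counts. The documents support neither reading. The row needs four things together: calcium below ULN, calcium down by more than 25%, uric acid above ULN, and uric acid up by more than 25%. From a baseline at or below ULN, the written rule already picks out only low values under the assumed ranges.

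It is also fair to say that low calcium is captured elsewhere. SAP Section 11.4 covers out-of-range values, Grade 3 or 4 abnormalities and worst grade. Section 11.4.2 adds grade shifts for serum chemistry in both phases and, for Phase 2, change from baseline by visit. Section 11 rules out inferential analysis of safety data.

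Finally, LLN is not the only possible repair, since the potassium and magnesium rows use other kinds of low criterion.

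All of this limits the size of the point. None of it makes an upper limit a sensible bound for a low-direction event, and nothing else in the SAP overrides the row.

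**Conclusion.** The row is wrong as written, very probably through a copying slip, and the consequence is small. The result can change only for a subject who starts above LLN/0.75 (about 1.08 to 1.15 × ULN under the assumed ranges), falls by more than 25% yet stays at or above LLN and below ULN, and meets the uric acid condition at the same time.

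The documents say nothing about how common raised baseline calcium is in this population, so no count can be given; it may be zero. A reader might infer that the reported proportion will be wrong. The supportable statement is that it could differ in rare cases.

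The agreement for baselines at or below ULN rests on LLN being at least 0.75 × ULN. That held in all seven assumed ranges, where LLN/ULN ran from 0.81 to 0.86. The primary endpoint, its test, the power and the sample size are untouched.

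**What to change.** In Table 5, change the calcium limit from <ULN to <LLN and add LLN to the list of abbreviations. A CTCAE hypocalcemia grade, in the style of the magnesium row, would serve equally well. The change to the SAP is one term and one abbreviation. It needs no new data, because Section 11.4 already uses normal ranges and CTCAE grades.

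The protocol's amendment rationale records that the primary clinical study report was final as of 15 Dec 2020. The sponsor should therefore also confirm which limit was programmed. If it was <ULN, rerun this one row. If it was a lower limit, the SAP text alone needs correcting.
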